7.5.1 Primary Endpoint

7.5.1.1 Composite Complete Remission (CRc) Rate

CRc rate is defined as the proportion of patients achieving CR or CRi prior to the start of subsequent anticancer therapy or stem cell transplant. Patients whose disease response cannot be assessed will be considered non-responders in the calculation of CRc rate. The CRc rate and the 2-sided 95% CI will be summarized by treatment group.

7.5.1.2 Overall Survival (OS)

Overall survival (OS) is defined as the time from randomization to death due to any cause. Specifically,

$$\text{OS} = \text{Date of death} - \text{Date of randomization} + 1.$$

For a patient who is not known to have died by the end of study follow up, observation of OS is censored on the date the patient was last known to be alive (i.e., date of last contact). Patients lacking data beyond the day of randomization will have their survival time censored on the date of randomization (i.e., OS duration of 1 day).

Specifically, censored OS will be calculated as:

$$\text{Censored OS} = \max(1, \text{last contact date} - \text{date of randomization} + 1),$$

The Kaplan-Meier method will be used to estimate OS. Kaplan-Meier curves depicting OS in the two arms will be generated. Additionally, the median OS, and survival rates at 30 days, 60 days, 3 months and every 3 months thereafter to the end of the follow-up period will be reported. The associated two-sided 95% CIs will be calculated.

Subgroup analysis of OS will be performed by the stratification factors and may be performed for the subgroups specified in Section 6.8.

7.5.2 Secondary Endpoints

7.5.2.1 Minimum Residual Disease-Negative CRc Rate

MRD-negative CRc rate is defined as the proportion of patients achieving both morphologic remission (CR or CRi) and MRD-negative status prior to the start of subsequent anticancer therapy or stem cell transplant. Patients whose morphologic response or MRD status cannot be assessed will be considered non-responders in the calculation of MRD-negative CRc rate. The MRD-negative CRc rate and the 2-sided 95% CI will be summarized by treatment group.

7.5.2.2 Duration of Remission

Duration of remission will be not analyzed given the limited follow-up of the study.

7.5.2.3 Event-Free Survival (EFS)

EFS will not be analyzed given the limited follow-up of the study.

7.5.2.4 Leukemia-Free Survival (LFS)

LFS will not be analyzed given the limited follow-up of the study.

7.5.2.5 Time to Complete Remission

Time to complete remission will not be analyzed given the limited follow-up of the study.

7.5.2.6 Mortality Rate

The 30-day mortality rate is defined as the proportion of patients who die within 30 days of randomization. The 60-day mortality rate is defined as the proportion of patients who die within 60 days of randomization. The 30-day and 60-day mortality rates and the associated 95% CIs will be summarized by treatment group. In addition, the cause of early mortality will be summarized by descending MedDRA preferred term and treatment group.

7.6 Safety Analyses

The safety analysis set will be used to summarize all safety endpoints.

Adverse events will be coded using the Medical Dictionary for Regulatory Activities (MedDRA, Version 19.0 or higher).

Laboratory values will be graded according to the National Cancer Institute (NCI) Common Terminology Criteria for Adverse Events (CTCAE version 4.03 or higher).

Concomitant medications will be coded using the WHO Drug Dictionary (version: June 2015 or more recent).

7.6.1 Adverse Events

Adverse events (AEs) will be summarized by descending MedDRA preferred term (PT) unless otherwise specified. For incidence reporting, if a patient reports more than one AE that was coded to the same system organ class (SOC) or PT, the patient will be counted only once for that specific SOC or PT.

A treatment-emergent AE is defined as a newly occurring or worsening AE after the first dose of any study treatment. See Appendix C for details regarding treatment-emergent classification. Summaries of AEs will be provided by treatment group and total for the following:

- Pre-existing AEs
- All treatment-emergent AEs

- AEs related to blinded study treatment
- AEs related to azacitidine
- AEs related to decitabine
- Serious Adverse Events (SAEs)
- SAEs related to blinded study treatment
- SAEs related to azacitidine
- SAEs related to decitabine
- AEs leading to blinded study treatment dose delay
- AEs leading to azacitidine dose delay
- AEs leading to decitabine dose delay
- AEs leading to blinded study treatment dose reduction
- AEs leading to azacitidine dose reduction
- AEs leading to decitabine dose reduction
- AEs leading to overall treatment discontinuation
- AEs leading to blinded study treatment discontinuation
- AEs leading to azacitidine discontinuation
- AEs leading to decitabine discontinuation
- Grade 3 or higher treatment-emergent AEs
- Infusion-related reactions (within 24 hours of blinded study drug dose)
- Treatment-emergent AEs by SOC and PT
- Treatment-emergent AEs by SOC, PT, and maximum severity. At each SOC or PT, multiple occurrences of events within a patient are counted only once at the highest severity
- Grade 3 or higher treatment-emergent AEs by SOC and PT
- TEAEs with incidence $\geq 5\%$ by SOC and PT
- SAEs with incidence $\geq 5\%$ by SOC and PT

AEs in the categories below as defined by the Standardized MedDRA Queries (SMQs) or customized searches will be summarized by SOC, PT, and maximum severity. SAEs will be summarized by PT.

- Serious infection
- Bleeding
- Thrombocytopenia
- Neutropenia
- Anemia
- Hepatotoxicity
- Edema
- Pulmonary
- Cardiomyopathy
- Cardiac failure
- Myocardial infarction

All AEs, SAEs, grade 3 or higher treatment-emergent AEs, AEs leading to treatment discontinuation, and AEs with fatal outcome will be listed.

7.6.2 Clinical Laboratory Parameters

Clinical laboratory data (hematology and serum chemistry) will be summarized by treatment group and total. Summary statistics of actual value and change from baseline will be presented by scheduled visit. In addition, laboratory data will be summarized in shift tables comparing the baseline value to the worst post-baseline value by NCI CTCAE grade for each parameter.

All clinical laboratory data and NCI CTCAE grades will be presented in data listings. A separate listing of laboratory results with CTCAE grade 3 or higher will also be presented. Normal ranges will be documented and out-of-range values will be flagged.

Patients with the liver function test results (AST, ALT, ALP, and total bilirubin) meeting the Hy's law will be listed.

7.6.3 ECOG Performance Status

ECOG performance status will be summarized for each visit by treatment group and total. Shifts from baseline to the best and worst post-baseline scores will be tabulated.

7.6.4 Concomitant Medications

Concomitant medications will be summarized by the WHO Drug substance name by treatment group and total, and listed by patient.

The number and percentage of patients who receive myeloid growth factor as a concomitant medication and the reason for administration will be summarized by treatment group and total.

7.6.5 Deaths

The number of total deaths, deaths that occurred within 30 days of last study treatment, and deaths that occurred more than 30 days after last study treatment, as well as the relationship to disease, will be summarized by treatment group and total. In addition, cause of death will be identified by descending MedDRA preferred term (unless otherwise specified) and summarized by treatment group and total. Death information will be listed by patient.

7.7 Additional Analyses

7.7.1 Stem Cell Transplant

Patients who received stem cell transplant after study treatment discontinuation will be listed, including the reason patient became eligible for transplant, the level of match of the donor, time from last dose of blinded study treatment to transplant, and transplant conditioning regimens administered.

7.7.2 Pharmacokinetics

The observed plasma vadastuximab talirine ADC and SGD-1882 may be summarized with descriptive statistics at each PK sampling time point. Any additional PK and PK/PD analyses may be performed and presented in a separate report.

7.7.3 Antitherapeutic Antibody Incidence Rate

The antitherapeutic antibody (ATA) incidence rate is defined as the proportion of patients who develop ATA at any time during the study. The ATA incidence rate will be summarized by treatment group and total.

7.7.4 Biomarker Analyses

Biomarker assessments may be summarized using descriptive statistics. The relationship between biomarkers and efficacy and safety endpoints may be explored and presented in a separate report.

8 INTERIM ANALYSIS

Due to safety concerns raised by the IDMC, the study was terminated early prior to the formal interim analyses planned in the protocol. No interim analyses will be conducted. Final analysis will be performed based on 240 patients randomized into the study by the time enrollment was closed.

9 CHANGES FROM PLANNED ANALYSES

9.1 Changes from the Protocol

Not Applicable.

9.2 Changes from the Original SAP

9.2.1 Version 2 Changes

The SAP was updated to reflect changes in protocol amendment 2 and to add additional details to the analysis. Changes from version 1 are summarized below:

- Sec 2.2, 3.2, 5.2, 5.3, and 7.5.2.4: update per protocol amendment 2
 - Add “duration of remission” as secondary objective/endpoint
 - Add mITT analysis set and clarify the definition of safety analysis set
- Sec 6.2: clarify the 12-month follow-up is from the last patient enrolled to the final analysis of OS after approximately 334 deaths occurred.
- Sec 6.5 and Appendix B: add language on missing data handling for subsequent anticancer therapy start date
- Sec 6.8: add additional subgroups to allow subgroup analysis
- Sec 7.5 and 7.6: add additional details to efficacy and safety analysis and data presentation
- Sec 7.7.4 and 7.7.5: add additional analysis for subsequent anticancer therapy and stem cell transplant

9.2.2 Version 3 Changes

The SAP was updated to reflect changes in protocol amendment 3 and to add additional details to the analysis. Changes from version 2 are summarized below:

- Sec 2.1, 2.2, 3.1, 3.2, 7.5.1 and 7.5.2: update per protocol amendment 3 to change the CRc rate from a secondary endpoint to an independent primary endpoint and to clarify that the MRD-negative CRc rate will be compared between the treatment arms
- Sec 6.2, 6.7, 6.10, and 8: update the sample size, multiplicity strategy, timing of the analysis, and interim analysis to account for 2 independent primary endpoints
- Sec 6.8: add additional subgroups to allow subgroup analysis
- Sec 7.4: add additional details for the calculation of duration of therapy
- Sec 7.6.1: add analysis for AEs of special interest (i.e., hepatobiliary AEs)
- Sec 7.6.3: add analysis for vital sign measurements
- Sec 7.7.5: add analysis for SOS/VOD

9.2.3 Version 4 Changes

The study was terminated early due to safety concerns raised by the IDMC. The SAP was updated to include only analyses required for the abbreviated CSR. Changes from version 3 are summarized below:

- Sec 6.7: Clarify that all efficacy analyses will be descriptive in nature and no multiple testing procedure will be applied
- Sec 6.10: Clarify that no interim analysis will be conducted and final analysis will be based on 240 patients randomized into the study by the time enrollment was closed
- Sec 7.1: Remove the summary of screen failed patients
- Sec 7.5: Remove all efficacy analyses other than the descriptive summary of CRc rate, OS, MRD-neg CRc rate, and early mortality rate
- Sec 7.6.1: Add additional summary of AEs of special interest
- Sec 7.6.2: Add additional summary to evaluate the extent of neutropenia
- Sec 7.7: Remove the analyses of PRO endpoints, transfusion, MRU, and subsequent therapy
- Sec 8: Clarify that no interim analysis will be conducted and final analysis will be based on 240 patients randomized into the study by the time enrollment was closed

9.2.4 Version 5 Changes

The SAP was updated to remove analyses that are limited by data availability as a result of early study termination. Changes from version 4 are summarized below:

- Sec 6.8: Remove subgroup analysis by FLT3 and ELN risk group
- Sec 7.2: Remove ELN risk group from disease characteristics summary
- Sec 7.4: Remove dose intensity summary for HMA because azacitidine and decitabine were administered according to package inserts
- Sec 7.6.2: Remove the exploratory analyses of laboratory results
- Sec 7.6.5: Remove the summary of growth factor cumulative dose
- Remove the vital signs listing

APPENDIX A: IMPUTATION OF PARTIALLY MISSING ADVERSE EVENT DATES

The algorithm below should be used to impute pre-existing condition and adverse event (AE) start dates for which only partial information is known. For ease of reading, both pre-existing conditions and AEs will be referred to as AE for the remainder of this document. The algorithm should be applied to every AE record on a record by record basis. AE start dates should be imputed before imputation of AE condition end date in all cases. The AE condition end date should only be used in the imputation of the AE start date if it a full known date.

AE day and month are missing

If the year is the same as the year of first dose of investigational agent and the onset period and/or onset time indicate that the start of the AE was pre-dose:

AE start date will be imputed as the minimum of (AE condition end date*, day prior to first dose of investigational agent)

If the year is the same as the year of first dose of investigational agent and the onset period and/or onset time indicate that the start of the AE was post-dose:

AE start date will be imputed as the minimum of (AE condition end date*, first dose date of investigational agent)

If the year is before the year of first dose of investigational agent:

AE start date will be imputed as the minimum of (AE condition end date*, December 31st see example 2 below)

If the year is after the year of first dose of investigational agent:

AE start date will be imputed as the minimum of (AE condition end date*, January 31st see example 2 below)

AE month only is missing

Treat day as missing and replace both month and day according to the above procedure

AE day only is missing

If the month/year is the same as the month/year of first dose of investigational agent and the onset period and/or onset time indicate that the start of the AE was pre-dose:

AE start date will be imputed as the minimum of (AE condition end date*, day prior to first dose of investigational agent)

If the month/year is the same as the month/year of first dose of investigational agent and the onset period and/or onset time indicate that the start of the AE was post-dose:

AE start date will be imputed as the minimum of (AE condition end date*, first dose date of investigational agent)

If the month/year is before the month/year of first dose of investigational agent:

AE start date will be imputed as the minimum of (AE condition end date*, last day of the month)

If the month/year is after the month/year of first dose of investigational agent:

AE start date will be imputed as the minimum of (AE condition end date*, last day of the month)

* only use condition end date if known and full end date is available.

The following algorithm should be used to impute AE condition end dates. The AE records for a condition/event should be sorted by the imputed start dates then record position (order of entry into the eCRF). After sorting, if any condition end date month/year is greater than any subsequent record end date month/year, then change the imputed start day only to end of month. Repeat as necessary.

After sorting the AE records, apply the following rules to partial or missing AE condition end dates:

For all records excluding the last chronological record for a condition/event

AE condition end date will be imputed as the start date of the subsequent record

For the last chronological record for a condition/event

If outcome is “recovered/resolved”, ”recovered/resolved with sequelae”, or “fatal” apply the following:

- If only year is provided for the end date and year is equal to the year of the last dose date:
 - AE condition end date will be imputed as the minimum of (last dose date + 30, death date, data extraction date, December 31st of the end date year)
- If only year is provided for the end date and year is not equal to the year of the last dose date:
 - AE condition end date will be imputed as the minimum of (death date, data extraction date, December 31st of the end date year)
- If month and year are provided for the end date:
 - AE condition end date will be imputed as the minimum of (death date, data extraction date, last day of the end date month/year)

If outcome is “recovering/resolving”, “not recovered/resolved”, “unknown”, or blank:

AE condition end date will not be imputed.

Example 1

AESPID 1: Condition/Event HEADACHE

First dose date 01JAN2012

Prior to imputation

Start date	Condition end date	Severity	Outcome	Onset
UNUNK2011	15APR2012	1	not recovered/not resolved	pre-ICF
15APR2012	UNMAY2012	2	recovering/resolving	post 1st dose
UNMAY2012	UNJUN2012	1	not recovered/resolved	post 1st dose
UNJUN2012	UNJUN2012	3	recovering/resolving	post 1st dose
UNJUN2012	10JUL2012	2	recovering/resolving	post 1st dose
10JUL2012	--	1	not recovered/not resolved	post 1st dose

Post imputation

Start date	Condition end date	Severity	Outcome
31DEC2011	15APR2012	1	not recovered/not resolved
15APR2012	31MAY2012	2	recovering/resolving
31MAY2012	30JUN2012	1	not recovered/not resolved
30JUN2012	30JUN2012	3	recovering/resolving
30JUN2012	10JUL2012	2	recovering/resolving
10JUL2012	--	1	not recovered/not resolved

Example 2 (highlights choice of last day of the month as opposed to the 1st or the 15th)

AESPID 4: Condition/Event NAUSEA

First dose date 01APR2012

Prior to imputation

Start date	Condition end date	Severity	Outcome	Onset
UNUNK2011	25APR2012	1	not recovered/resolved	pre-ICF
25APR2012	UNAPR2012	2	recovering/resolving	post 1st dose
UNAPR2012	04MAY2012	1	recovered/resolved	post 1st dose

Post imputation

Start date	Condition end date	Severity	Outcome
31DEC2011	25APR2012	1	not recovered/not resolved
25APR2012	31APR2012	2	recovering/resolving
31APR2012	04MAY2012	1	recovered/not resolved

APPENDIX B: IMPUTATION OF PARTIALLY MISSING SUBSEQUENT ANTICANCER THERAPY START DATE

The algorithm below should be used to impute subsequent anticancer therapy start dates for which only day is missing.

- If the month and year of the subsequent anticancer therapy start date is the same as the month and year of the response assessment date, and the response is a disease progression or relapse:
 - Subsequent anticancer therapy start date will be imputed as the date of response assessment.
- If the month and year of the subsequent anticancer therapy start date is the same as the month and year of the response assessment date, and the response is not a disease progression or relapse:
 - Subsequent anticancer therapy start date will be imputed as the first day of the month.

APPENDIX C: DEFINITION OF THE TERM “TREATMENT-EMERGENT” WITH RESPECT TO AE CLASSIFICATION

The algorithm below should be used to determine whether an adverse event (AE) is classified as a treatment-emergent adverse event (TEAE). A TEAE is defined as any AE which is newly occurring or worsening in severity, where newly occurring means that the AE was not present at baseline. For ease of reading, both pre-existing conditions and AEs will be referred to as AEs for the remainder of this document. AE dates should be imputed in accordance with the algorithm detailed in Appendix A prior to determination of TEAE classification. Details of the TEAE classification are as follows:

- 1) Determine the first/earliest dose date/time of any study treatment (for combination studies this includes any component of the regimen)
- 2) Classify an AE as a baseline AE if it satisfies both of criteria a and b below:
 - a) The onset period field is: “started before the signing of informed consent”; or “started after consent but before the first dose of any study treatment”; or, the onset period field is missing and the AE start date is prior to the first dose date of any study drug(step 1, above).
 - b) The stop date satisfies either of i or ii below:
 - i) The stop date is the same as or a later date than the first dose date of any study treatment
 - ii) The stop date is missing with outcome equal to: recovering/resolving (this outcome may or may not be associated with a date); or not recovered/not resolved; or unknown.
 - iii) Note: if the AE has no outcome or stop date provided it should be queried
 - c) Note: If the event ended on Day 1 (the date of first dose of any study drug) it will be considered a baseline event.
- 3) Classify an AE as post-baseline if it meets either of criteria a or b below:
 - a) The onset period of the AE is “started after the first dose of any study treatment”
 - b) The onset period of the AE is missing and the AE start date is the same as or a later date than the first dose date of any study treatment
- 4) Compare post-baseline AEs to baseline AEs using the lower level term (LLT). **If the post-baseline AE meets any of the following criteria then classify it as a TEAE:**
 - a) There is a baseline AE with the same LLT but the post-baseline AE has a greater CTC grade.
 - b) There are no baseline AEs with a matching LLT for the post-baseline AE.
 - c) The post-baseline AE is uncoded.

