## 4.2 Exclusion Criteria

1. AML associated with favorable risk karyotypes including inv(16), t(8;21), t(16;16), or t(15;17).
2. Patients who are medically fit and willing to receive standard intensive induction chemotherapy.

3. Patients who are candidates for allogeneic stem cell transplant at the time of enrollment.
4. Patients with a history of one of the following myeloproliferative neoplasms: essential thrombocythemia, polycythemia vera, and primary myelofibrosis.
5. Received prior treatment with HMA or chemotherapy for antecedent MDS. Prior hydroxyurea or 6-mercaptopurine is permitted, as is prior lenalidomide treatment for MDS.
6. History of allogeneic stem cell transplant.
7. History of clinically significant chronic liver disease (e.g. liver cirrhosis) and/or ongoing alcohol abuse.
8. Patients with supplemental oxygen requirement or resting oxygen saturation of <90%.
9. Concurrent active malignancy other than nonmelanoma skin cancer or carcinoma in situ of the following: bladder, stomach, colon, cervix, endometrium, melanoma, or breast. Patients with previous malignancies are eligible if the malignancy has been confined and surgically resected (or treated with other modalities) with curative intent. Any active systemic therapy must have been completed >1 year from enrollment (except for hormonal/anti-hormonal treatment, e.g. breast cancer).
10. Central nervous system leukemia based on imaging or documented positive cytology in cerebral spinal fluid.
11. Any uncontrolled Grade 3 or higher (per NCI CTCAE, Version 4.03) viral, bacterial, or fungal infection within 14 days prior to the first dose of study treatment. Antimicrobial prophylaxis or ongoing treatment of resolving/controlled infection is permitted.
12. Patients with any of the following:
  - Known positive hepatitis B polymerase chain reaction (PCR) assay who have also tested positive for hepatitis B surface antigen and/or anti-hepatitis B core antibody; patients with a negative PCR assay are permitted with appropriate antiviral prophylaxis.
  - Known or suspected active hepatitis C infection (positive by PCR or on antiviral therapy within the last 6 months).
  - Known human immunodeficiency virus (HIV) infection.

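### SAP Appendix C does not count a same- or lower-grade recurrence as treatment-emergent, even when the baseline event had resolved first

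*SAP*

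**What the plan says.** SAP 7.6.1 gives the general definition: "A treatment-emergent AE is defined as a newly occurring or worsening AE after the first dose of any study treatment". Protocol 9.3.9.2 is similar. SAP 7.6.1 sends the reader to Appendix C for the algorithm, and Appendix C narrows the first half of the definition: "newly occurring means that the AE was not present at baseline".

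The steps that matter are these.

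- **Step 2** makes a pre-dose event a baseline event if it is still unresolved with no stop date, or if "The stop date is the same as or a later date than the first dose date of any study treatment". A note adds: "If the event ended on Day 1 (the date of first dose of any study drug) it will be considered a baseline event".
- **Step 3** makes an event with onset after first dose a post-baseline event.
- **Step 4** has three criteria, any one of which makes a post-baseline event treatment-emergent. Criterion (b) takes in events whose LLT was not recorded at baseline, and criterion (c) takes in uncoded events. When the LLT was recorded at baseline, only criterion (a) is left: "There is a baseline AE with the same LLT but the post-baseline AE has a greater CTC grade".

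No criterion in step 4 looks at the end date or outcome of the baseline event. Six of the summaries listed in SAP 7.6.1 are worded as treatment-emergent, two of them restricted to Grade 3 or higher.

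**The concern.** An event that was present at first dose, resolved, and came back weeks later on treatment would ordinarily be read as a new occurrence. Appendix C treats it as if the baseline event had never ended, unless the new episode is more severe.

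This population can meet the condition. Protocol 4.1 sets no minimum neutrophil or platelet count. Protocol 7.7.1.1 has all conditions present before the first dose recorded. Exclusion criterion 11 says that "ongoing treatment of resolving/controlled infection is permitted". A patient could enter with a recorded Grade 4 cytopenia, recover, and become Grade 4 again on treatment. Protocol Table 1 gives Grade 3 or higher neutropenia or thrombocytopenia without leukemia its own row, separate from the same finding with persistent leukemia, so the protocol itself treats the two as different events.

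The trial stopped for safety, and SAP 6.7 makes all efficacy analysis descriptive. The AE tables therefore carry much of the weight of the abbreviated report.

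**Working it through.** The plan states no figure on this point, so the check is to run Appendix C as written and see which events it counts.

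**Set-up.** One baseline event of grade g (1 to 4) and one later episode of grade h (1 to 5), same LLT, coded, starting on Day 40. The baseline event ends on Day −2, Day 1 or Day 10, or never. With several baseline records of one LLT, step 4a does not say which grade governs, so the check uses one.

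**Baseline event ends on Day 10.** Day 10 is later than first dose, so step 2 makes it a baseline event. Step 3 makes the Day 40 episode post-baseline. Criterion (b) fails because a match exists, and (c) fails because the event is coded. Only (a) is left, so the episode counts if and only if h > g.

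- All pairs: 4 × 5 = 20. Not counted (h ≤ g): 1 + 2 + 3 + 4 = 10.
- Pairs with h of 3 or more: 4 × 3 = 12. Not counted: (g, h) = (3,3), (4,3), (4,4), which is 3.

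These are counts of possible pairs, not of patients.

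**The other cases**

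| Baseline event | Day 40 episode, same LLT | Pairs not counted | With an added resolution criterion |
|---|---|---|---|
| Ended Day −2 | Always counted, by (b) | 0 of 20 | 0 |
| Ended Day 1 | Counted only if h > g | 10 of 20 | 0 |
| Ended Day 10 | Counted only if h > g | 10 of 20 | 0 |
| Never ended | Counted only if h > g | 10 of 20 | 10 (unchanged) |

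An episode with a different LLT, or in a patient with no matching baseline event, always counts. The first two rows show the anomaly: whether the earlier event ended on Day −2 or Day 1 decides how a same-grade episode on Day 40 is classified.

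**Laboratory tables.** SAP 7.6.2 shifts baseline grade to worst post-baseline grade. Grade 4, recovery, then Grade 4 again is shown as 4 to 4, exactly as for a patient who never recovered. The shift table cannot separate recurrence from persistence.

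**Size, as illustration only.** Let I be the share of patients with the event on treatment. Let b be the share of those who entered with a matching event of equal or higher grade that later resolved. If none of them has another qualifying record, the table shows I × (1 − b), and the maximum loss is 120 × I × b patients. The 120 per arm assumes an even split of the 240 randomized. I is borrowed from the Grade 3 or higher rates of the phase 1 combination cohort (Protocol 1.5): febrile neutropenia 46%, neutropenia 25%. The documents do not give b; 0 to 30% is assumed.

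| b | I = 46%: shown (patients lost of 120) | I = 25%: shown (patients lost of 120) |
|---|---|---|
| 0% | 46.0% (0) | 25.0% (0) |
| 5% | 43.7% (2.8) | 23.75% (1.5) |
| 10% | 41.4% (5.5) | 22.5% (3.0) |
| 20% | 36.8% (11.0) | 20.0% (6.0) |
| 30% | 32.2% (16.6) | 17.5% (9.0) |

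**The case against.** **There is no contradiction inside the SAP.** SAP 7.6.1 defers to Appendix C, which defines its own term. That stands: the point is a gap in the rule, not two conflicting rules. But neither document gives a reason for leaving out an episode that began after recovery.

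**The conditions are narrow.** This also stands. The patient needs a baseline event with the same LLT, at an equal or higher grade, that lasted to first dose and then resolved. Patients are counted once per preferred term, so one other qualifying record restores them. Exclusion criterion 11 bars uncontrolled Grade 3 or higher infection in the 14 days before first dose. Protocol 7.7.1.1 says that a laboratory value is in general not recorded as an AE unless it has clinical consequences, so fewer baseline cytopenias may be on the form.

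**Other outputs show the events.** As worded, the tables of serious events, dose delay, reduction and discontinuation, and the SMQ or custom categories (neutropenia, thrombocytopenia and serious infection among them) are not limited to treatment-emergent events. All AEs are listed. This stands and limits the harm. It does not repair the treatment-emergent tables, which may then fail to reconcile with the others.

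**Stronger readings.** A reader might infer that recurrent cytopenias, febrile neutropenia and infections vanish as classes from the treatment-emergent tables. The conditions above show that they do not. A reader might also infer that more events are hidden in the experimental arm, because the design expects a composite remission rate of 40% against 20%. That treats remission as count recovery. Under Protocol Appendix E it includes remission with incomplete neutrophil or platelet recovery, and 10 of the 15 phase 1 remissions were of that kind. The documents give no recurrence rate by arm.

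**Conclusion.** The gap is real and can be read directly from steps 2 and 4 of Appendix C. A same-LLT episode at the same or a lower grade is never treatment-emergent once a matching event was present at first dose, however clearly that event resolved. This can understate treatment-emergent incidence and, in patients whose baseline event was already Grade 3 or 4, Grade 3 or higher incidence.

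The mechanism is certain; the size is not. The percentages worked out above rest on an assumed b and on borrowed phase 1 rates, and they are maximum losses. Neither the effect in this trial nor its direction between arms can be computed from the documents. The correction is still worth making, because it is cheap and safety is the reason the trial ended.

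**What to change.** Add a fourth criterion to step 4 of Appendix C: a post-baseline event is treatment-emergent, whatever its grade, if it starts after all baseline events with the same LLT have ended with outcome recovered or resolved, with or without sequelae. Appendix A's examples carry one event over several records as severity changes, so the end date and outcome should be taken from the last record of the event that began before first dose.

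Then re-run the treatment-emergent and Grade 3 or higher treatment-emergent tables, or keep the present rule and add a sensitivity table on the new one.

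Two wider changes should not be made. Counting any record whose grade exceeds the record just before it would label a baseline event that never resolved, and merely fluctuated, as treatment-emergent. Matching on preferred term instead of LLT would create more baseline matches and so, by itself, remove treatment-emergent events; LLT matching can stay.

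The cost is one sentence in the SAP and a small amount of programming. Onset and resolution dates, severity and outcome are already on the AE form (Protocol 7.7.1.2), so sites do nothing new. Treatment-emergent counts may rise slightly.
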